3.2. Study Duration for Subjects

The study is designed as a 1-year (52-week) study, with a 4-week Post-treatment Observational Follow-up Phase.

Visits will be scheduled at screening (no more than 5 weeks prior to randomization), Week 0 (baseline/randomization), Weeks 2, 4, 16, 20, 32, 44, and 52. Subjects who discontinue before

Week 52 will be asked to attend an Early Termination visit. A post-treatment observational follow-up will be conducted by phone at Week 56 for subjects who complete the 52-week study treatment, or 4 weeks after study treatment discontinuation.

3.3. End of Trial

The End of Trial is defined as either the date of the last visit of the last subject to complete the post-treatment follow-up, or the date of receipt of the last data point from the last subject that is required for primary, secondary, and/or exploratory analysis, as pre-specified in the protocol, whichever is the later date.

Approved

4. STUDY POPULATION

4.1. Number of Subjects

Approximately 255 subjects will be enrolled in the study across approximately 6 to 10 countries in Western Europe.

4.2. Inclusion Criteria

Subjects must satisfy the following criteria to be enrolled in the study:

1. Subject is \geq 18 years of age at the time of signing the informed consent form (ICF).
2. Subject must understand and voluntarily sign an ICF prior to any study-related assessments/procedures being conducted.
3. Subject is willing and able to adhere to the study visit schedule and other protocol requirements.
4. Subject has diagnosis of chronic plaque psoriasis for at least 6 months prior to baseline, that cannot be controlled by topical therapy.
5. Subject has a PASI score ranging from ≥ 3 to ≤ 10 at baseline.
6. Subject has a DLQI score > 10 at baseline.
7. Subject has presence of ≥ 1 clinical manifestations of plaque psoriasis, defined as at least one of the following:
 - a. Moderate to severe scalp psoriasis, defined as Scalp Physician Global Assessment (ScPGA) ≥ 3
 - b. Nail psoriasis, defined as onycholysis and onychodystrophy in at least 2 fingernails
 - c. Moderate to severe genital plaque psoriasis, defined as modified static Physicians Global Assessment of Genitalia (sPGA-G) ≥ 3
 - d. Moderate to severe palmoplantar psoriasis, defined as Palmoplantar Psoriasis Physicians Global Assessment (PPPGA) ≥ 3
 - e. Moderate to severe plaque psoriasis in visible locations (dorsal hand, face, neck, and hairline) with static Physicians Global Assessment (sPGA) ≥ 3
8. Subject must be in general good health (except for psoriasis) as judged by the Investigator, based on medical history, physical examination, and clinical laboratories. (NOTE: The definition of good health means a subject does not have uncontrolled significant co-morbid conditions.)
9. Subject must have failed to respond to, or be contraindicated to, or intolerant to other systemic therapy including, but not limited to, cyclosporine, methotrexate, acitretin, psoralen and ultraviolet-A-light (PUVA), fumaric acid esters or biologic therapies.
10. Subjects (**in Italy only**) must be non-responder to, contraindicated to, or intolerant to other systemic therapy (including cyclosporine, methotrexate, or PUVA) **AND** also be contraindicated to, or intolerant to biologics.

Approved

11. Females of childbearing potential (FCBP)[†] must have a negative pregnancy test at Screening and Baseline. While on investigational product and for at least 28 days after taking the last dose of investigational product, FCBP who engage in activity in which conception is possible must use one of the approved contraceptive[§] options described below:

Option 1: Any one of the following highly effective methods: hormonal contraception (oral, injection, implant, transdermal patch, vaginal ring); intrauterine device (IUD); tubal ligation; or partner's vasectomy;

OR

Option 2: Male or female condom (latex condom or nonlatex condom NOT made out of natural [animal] membrane [for example, polyurethane]) PLUS one additional barrier method: (a) diaphragm with spermicide; (b) cervical cap with spermicide; or (c) contraceptive sponge with spermicide.

NOTE: Option 2 may not be acceptable as a highly effective contraception option in all countries per local guidelines/regulations.

4.3. Exclusion Criteria

The presence of any of the following will exclude a subject from enrollment:

1. Subject has any condition, including other inflammatory diseases or dermatologic conditions, which confounds the ability to interpret data from the study, including other types of psoriasis (ie, erythrodermic, or guttate), other than plaque psoriasis or inverse psoriasis.
2. Subject has history of drug-induced psoriasis.
3. Subject has arthritis that requires disease-modifying antirheumatic drug (DMARD) treatment.
4. Subject unable to avoid use of tanning booths for at least 4 weeks prior to baseline and during study.
5. Subject is currently enrolled in any other clinical trial involving an investigational product.
6. Other than psoriasis, subject has history of clinically significant or uncontrolled disease (as determined by the Investigator), including the presence of laboratory abnormalities, cardiac, endocrinologic, pulmonary, neurologic, psychiatric, hepatic, renal, hematologic, immunologic disease, or other major disease, which places the subject at unacceptable risk if he/she were to participate in the study.

[†] A female of childbearing potential is defined as a sexually mature female who 1) has not undergone a hysterectomy (the surgical removal of the uterus) or bilateral oophorectomy (the surgical removal of both ovaries) or 2) has not been postmenopausal for at least 24 consecutive months (that is, has had menses at any time during the preceding 24 consecutive months).

[§] The female subject's chosen form of contraception must be effective by the time the female subject is randomized into the study (for example, hormonal contraception should be initiated at least 28 days before randomization).

7. Prior history of suicide attempt at any time in the subject's lifetime prior to signing the informed consent, or major psychiatric illness requiring hospitalization within the last 3 years prior to signing the informed consent.
8. Subjects with severe renal impairment, defined by eGFR (estimated glomerular filtration rate) or CLcr (creatinine clearance) less than 30 mL/min, are also categorized as having Stage 4 Chronic Kidney Disease (CKD), and are excluded from the study.
9. Malignancy or history of malignancy or myeloproliferative or lymphoproliferative disease within the past 3 years, except for treated (ie, cured) basal cell or squamous cell in situ skin carcinomas.
10. Bacterial infections requiring treatment with oral or injectable antibiotics, or significant viral or fungal infections, within 4 weeks of Screening. Any treatment for such infections must have been completed and the infection cured, at least 4 weeks prior to Screening and no new or recurrent infections prior to the Baseline Visit.
11. Subject has received a live vaccine within 3 months of baseline or plans to do so during study.
12. Subject is a pregnant or breastfeeding (lactating) woman.
13. Subject has used topical therapy within 2 weeks of randomization (including, but not limited to, topical corticosteroids, retinoids or vitamin D analog preparations, tacrolimus, pimecrolimus, anthralin/dithranol, or moisturizers which contain urea or salicylic acid). Use of phototherapy within 4 weeks prior to randomization. Use of conventional systemic therapy or systemic corticosteroids within 4 weeks prior to randomization, except for conditions other than psoriasis or psoriatic arthritis. Use of biologic therapy within 5 pharmacokinetic half-lives.
14. Prior treatment with apremilast, or participation in a clinical study, involving apremilast.
15. Subject has any condition that confounds the ability to interpret data from the study.
16. Subject has history of allergy or hypersensitivity to any components of the IP (including placebo).
17. Subject has rare hereditary problem of galactose intolerance, lapp lactase deficiency or glucose-galactose malabsorption.

Approved

5. TABLE OF EVENTS

Table 3: Table of Events

Visit Number	Screening	Placebo-Controlled Phase ^a					Apremilast Extension Phase ^b				Post-Treatment Observational Follow-up ^d
		1	Baseline 2	3	4	5	6	7	8	9/ET ^c	
Week	-35 to 0 days	0 (Day 1)	2 (± 3 days)	4 (± 3 days)	16 (± 3 days)	20 (± 4 days)	32 (± 4 days)	44 (± 4 days)	52 (± 4 days)		56 weeks (or 4 weeks after study discontinuation)
Informed consent ^e	X	-	-	-	-	-	-	-	-	-	-
Inclusion/Exclusion criteria	X	X	-	-	-	-	-	-	-	-	-
Demographics	X	-	-	-	-	-	-	-	-	-	-
Medical history	X	-	-	-	-	-	-	-	-	-	-
Prior / concomitant medications or therapies	X	X	X	X	X	X	X	X	X		-
Clinical and Laboratory Assessments											
Adverse events ^f	X	X	X	X	X	X	X	X	X	X	
Pregnancy test and contraception education ^g	X	X	-	-	-	-	-	-	X	-	
Vital signs	X	X	X	X	X	X	X	X	X	-	
Height	X	-	-	-	-	-	-	-	-	-	
Weight	X	X	X	X	X	X	X	X	X	-	
Waist Circumference	X	X	X	X	X	X	X	-	X	-	
Body Mass Index	X	-	-	-	-	-	-	-	-	-	
Physical Examination	X	-	-	-	-	-	-	-	-	-	
Clinical laboratory evaluations ^{h,i}	X	X	-	-	X	-	X	-	X	-	

Approved

Table 3: Table of Events (Continued)

Visit Number	Screening	Placebo-Controlled Phase ^a				Apremilast Extension Phase ^b				Post-Treatment Observational Follow-up ^d
	1	Baseline 2	3	4	5	6	7	8	9/ET ^c	
Week	-35 to 0 days	0 (Day 1)	2 (± 3 days)	4 (± 3 days)	16 (± 3 days)	20 (± 4 days)	32 (± 4 days)	44 (± 4 days)	52 (± 4 days)	56 (or 4 weeks after study discontinuation)
Health-related Quality of Life and Efficacy Assessments^j										
DLQI	X	X	X	X	X	X	X	-	X	-
sPGA of Visible Location ^k	X	X	X	X	X	X	X	-	X	-
ScPGA ^k	X	X	X	X	X	X	X	-	X	-
Nail Assessment ^l	X	X	X	X	X	X	X	-	X	-
NAPSI ^k		X	X	X	X	X	X	-	X	-
Modified sPGA-G ^k	X	X	X	X	X	X	X	-	X	-
PPPGA ^k	X	X	X	X	X	X	X	-	X	-
Itch NRS	-	X	X	X	X	X	X	-	X	-
Skin Discomfort/Pain VAS	-	X	X	X	X	X	X	-	X	-
PASI	X	X	X	X	X	X	X	-	X	-
BSA	-	X	X	X	X	X	X	-	X	-
EQ-5D	-	X	-	-	X	-	-	-	X	-
PNQ	-	X	-	-	-	-	-	-	-	-
PBQ	-	-	-	X	X	-	X	-	X	-
WPAI: PSO	-	X	-	-	X	-	-	-	X	-
Photography ^m	-	X	-	-	X	-	X	-	X	-

Approved

Table 3: Table of Events (Continued)

Visit Number	Screening 1	Placebo-Controlled Phase ^a				Apremilast Extension Phase ^b				Post-Treatment Observational Follow-up ^d 56 (or 4 weeks after study discontinuation)
		Baseline 2	3	4	5	6	7	8	9/ET ^c	
Week	-35 to 0 days	0 (Day 1) (± 3 days)	2 (± 3 days)	4 (± 3 days)	16 (± 3 days)	20 (± 4 days)	32 (± 4 days)	44 (± 4 days)	52 (± 4 days)	
Dispense IP	-	X	-	X	X	X	X	X	-	-
Return and Count IP Tablets	-	-	-	X	X	X	X	X	X	-

Abbreviations: BMI = body mass index; BSA = body surface area; [REDACTED] DLQI = Dermatology Life Quality Index; EQ-5D = European Quality of Life 5-Dimension; FCBP = females of childbearing potential; IP = investigational product; NAPSI = Nail Psoriasis Severity Index; PASI = Psoriasis Area Severity Index; PBQ = Patient Benefit Questionnaire; PNQ = Patient Needs Questionnaire; PPPGA = Palmoplantar Psoriasis Physicians Global Assessment; NRS = Numeric Rating Scale; ScPGA = Scalp Physician Global Assessment; sPGA = static Physicians Global Assessment; sPGA-G = static Physicians Global Assessment of Genitalia; VAS = Visual Analog Scale; WPAI:PSO = Work Productivity and Activity Impairment Questionnaire: Psoriasis.

^a Visits in the Placebo-controlled Phase to be performed ± 3 days.

^b Visits in the Apremilast Extension Phase to be performed ± 4 days.

^c Visit 9 will serve as the Early Termination Visit for any subject who prematurely discontinues from the study, prior to Week 52. All subjects who complete the study or discontinue the study early will be asked to enter the Four-week Post-treatment Observational Follow-up Phase.

^d Post-treatment observational follow-up will be conducted by telephone.

^e Written informed consent will be obtained by the Principal Investigator or designee prior to initiation of any study procedures, including washouts from prior medications.

^f Adverse event review should include new or worsening psychiatric symptoms, suicidal ideation, suicidal attempt, severe diarrhea, nausea and vomiting, and unexplained and clinically significant weight loss. See Section 6.5.

^g Females of childbearing potential (FCBPs) only. Serum pregnancy tests are performed at Screening, and Early Termination Visit/Last Treatment Visit. Urine pregnancy test kit will also be provided to the site and performed at baseline prior to randomization. The Investigator will educate all FCBP about the different options of contraceptive methods and their correct use at Screening and Baseline visits. The subject will be reeducated every time their contraceptive measures/methods or their ability to become pregnant changes. A pregnancy test(s) should be administered if the FCBP subject misses a menstrual period.

^h Laboratory assessments will include routine/standard chemistry and hematology panel of tests. A lipid panel will be included in the standard chemistry panel. If screening laboratory assessments are within 7 days of Baseline (Week 0), laboratory assessment does not need to be repeated at Baseline (Week 0). For females of childbearing potential urine pregnancy test will be performed at Baseline (Week 0) to confirm subject eligibility (negative results required for IP administration).

^j Subject assessments must be completed in the following order: DLQI, Itch NRS, Skin Discomfort/Pain VAS, EQ-5D, PNQ/PBQ, and WPAI: PSO, as scheduled in the Table of Events.

^k All manifestations should be assessed in all subjects at all visits, so that improvement, worsening, or new onset of any of these manifestations can be assessed.

^l Nail assessments will evaluate presence of nail psoriasis, defined as onycholysis and onychodystrophy.

^m Photographs will be obtained from subjects who provide separate consent to be photographed and at select sites only.

6. PROCEDURES

The following procedures will be conducted as outlined in the Table of Events, [Table 3](#).

6.1. Screening Period

Screening evaluations will be performed for all subjects to determine study eligibility. These evaluations must be completed within 5 weeks of randomization. Subjects who do not meet eligibility criteria for the study may be re-screened once, after a minimum of 35 days from the date of their first screening.

Waivers to the protocol will not be granted during the conduct of this trial, under any circumstances.

Safety laboratory analyses and all assessments will be performed (locally/centrally). Screening laboratory values must demonstrate subject eligibility, but may be repeated once within the screening window, if necessary.

The following will be performed at screening as specified in the Table of Events, after informed consent has been obtained:

- Demographics (year of birth, sex, and race, if allowed by local regulations, will be collected).
- Complete medical history
- Prior and concomitant medications
- Physical examination, height, weight, waist circumference, body mass index (see [Appendix O](#))
- Vital signs (including blood pressure and heart rate)
- Hematology panel including complete blood count (CBC) with differential, including red blood cell (RBC) count, hemoglobin, hematocrit, mean corpuscular hemoglobin (MCH), mean corpuscular hemoglobin concentration (MCHC), RBC Morphology, mean corpuscular volume (MCV), white blood cell (WBC) count (with differential), and platelet count.
- Chemistry panel including sodium, potassium, calcium, chloride, blood urea nitrogen (BUN), creatinine, creatinine clearance, glucose, albumin, total protein, alkaline phosphatase, bilirubin (total and direct), aspartate aminotransferase/serum glutamic oxaloacetic transaminase (AST/SGOT), alanine aminotransferase/serum glutamic pyruvic transaminase (ALT/SGPT), gamma-glutamyl transferase (GGT), lactate dehydrogenase (LDH). A lipid panel will be included in the standard chemistry panel. [REDACTED]
- Pregnancy test is required for all female subjects of childbearing potential. Serum beta human chorionic gonadotropin (β -hCG) pregnancy test will be performed at screening. Urine (or serum) pregnancy test will be performed to assess subject eligibility within 72

Approved

hours prior to the first administration of IP, if the initial serum pregnancy test did not already occur with 72 hours of dosing (negative results required for IP administration).

- Contraception education will be performed by the Investigator at screening for all FCBP about the options for and correct use of contraceptive methods at the Screening and Baseline Visits and at any time when a FCBP's contraceptive measures or ability to become pregnant changes.
 - A pregnancy test should be performed if the FCBP subject has missed a menstrual period or the contraception method has changed
 - Counseling about pregnancy precautions and the potential risks of fetal exposure must be conducted.
- Adverse event assessment begins when the subject signs the informed consent form
- Health-related quality of life and efficacy assessments to determine study eligibility, including DLQI, sPGA of visible locations, ScPGA, NAPSI, modified sPGA-G, PPPGA, and PASI

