5.4. Definition of baseline

Core baseline (Week 0) is used for all efficacy analyses, safety analyses for the placebo-controlled period, and summary of baseline disease characteristics.

For efficacy analysis and summary of baseline disease characteristics data, baseline is defined as the last value measured prior to or at the randomization visit.

For safety summaries, baseline is defined as the last value measured on or before the day of the first dose of double-blind treatment.

Apremilast treatment baseline is used for the summaries of safety analyses for the Apremilast Exposure Period. It is defined as the last value measured on or before the day of the first Apremilast dose.

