9.3. Analysis of Primary Efficacy Endpoint

The primary endpoint is subjects achieving DLQI response at Week 16 (defined as ≥ 4 -point reduction in DLQI from baseline at Week 16). The primary endpoint will be analyzed using the ITT population. A supplemental analysis will be performed using the PP population.

The treatment difference in proportions of DLQI response between Apremilast 30 mg BID and placebo will be compared using CMH test adjusted for the stratification factor at randomization

Apremilast

Statistical Analysis Plan. Protocol CC-10004-PSOR-020

Amgen INC.

(i.e., the 5 difficult to treat manifestation types). This form of the CMH test will use the sample sizes in each of the strata as weights when estimating the adjusted difference in the treatment proportions, constructing 95% Wald confidence intervals for the difference, and conducting a statistical test of no difference between the treatment proportions (i.e., $H_0: \pi_{APR} - \pi_{PBO} = 0$ as the null hypothesis). The difference of the response rate (Apremilast 30 mg BID - placebo) and its 95% CI as well as the p-value will be produced using the Cochran-Mantel-Haenszel (CMH) test and adjusting for the stratification factor at randomization (i.e., the manifestations of scalp psoriasis, nail psoriasis, palmoplantar psoriasis, genital psoriasis, or psoriasis in visible locations). SAS PROC FREQ with the COMMONRISKDIFF (TEST=MH) option will be used for the analysis.

All reasonable attempts will be made to prevent missing data from occurring in the study. However, in the case of missing data at Week 16, a multiple imputation (MI) method (SAS Institute Inc. 2008) will be incorporated as the primary analysis. such that unbiased estimation and valid statistical inferences (i.e., confidence intervals and hypothesis testing) can be made.

The SAS procedure MI will be used to impute missing DLQI scores at the scheduled assessments in the Placebo-controlled Phase (Weeks 0 to 16) to create M=25 complete data sets. The missing data patterns will be checked by treatment and stratification factor at the core baseline (Week 0), Week 2, Week 4, and Week 16. If there are non-monotone missing patterns, two separate imputation procedures will be used to complete the imputation process.

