In the first step, the Markov Chain Monte Carlo (MCMC) method will be used to impute missing scores by treatment and stratification factor to create M=25 imputed data sets with monotone missing patterns. The minimum and the maximum values for imputation will be 0 and 30, which correspond to the lowest and the highest DLQI scores. The seed will be set to 804529, the imputed values will be rounded to integers and a single chain will be used to produce imputations. In case there are convergence issues, the imputation will be done by treatment only. If the convergence issue remains, then the imputation will be done on data pooled from both treatment arms.

In the second step, the predictive mean matching method will be used to impute the remaining missing values for the 25 data sets with monotone missing patterns. The MONOTONE REGPMM statement will be used with seed 447159. The missing values at each visit will be imputed based on treatment, stratification factor, and DLQI scores at the core baseline and previous visits. In presence of convergence issue, a simplified regression model without stratification factor will be used. The number of closest observations to be used in the selection will be K=5.

After the completion of imputation made on the continuous-like scale of the total DLQI score, the primary endpoint will then be derived by dichotomizing the DLQI score prior to performing the CMH analysis described above. The same CMH method will be used to analyse the 25 complete data sets and the SAS procedure MIANALYZE will be used to combine the results for the statistical inferences.

In addition to the primary analysis using MI method and the supplemental analysis in PP population, the following supportive analyses using CMH method for the primary endpoint will be performed for: (1) ITT population treating missing values using the last observation carried

Apremilast

Statistical Analysis Plan. Protocol CC-10004-PSOR-020

Amgen INC.

forward (LOCF) method, (2) ITT population treating missing values using the non-responder imputation (NRI) method.

In order to assess the impact of Covid-19 on the DLQI data collection, a sensitivity analysis will be conducted by excluding the data collected via paper version of the DLQI questionnaire.

Similar analysis planned for Week 16 will be repeated for DLQI response at Week 2 and Week 4.

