9.4.1. Secondary Efficacy Endpoints in the Placebo-controlled Phase

All analyses will be conducted using ITT population including data from the Placebo-controlled Phase (Week 0 to Week 16). Table 5 is the summary on how the secondary efficacy endpoints at Week 16 will be analyzed.

Table 5 Analysis on the Secondary Efficacy Endpoints at Week 16

Summary Measure of Endpoint	Primary Analysis	Supportive Analysis
Mean change from baseline in DLQI at Week 16	ANCOVA model adjusted by baseline DLQI score, treatment, stratification factor on data with MI	ANCOVA model adjusted by baseline DLQI score, treatment, stratification factor on data with LOCF
Mean percent change in Body Surface Area (BSA) affected by psoriasis at Week 16	ANCOVA model adjusted by BSA score, treatment, stratification factor on data with MI	ANCOVA model adjusted by BSA score, treatment, stratification factor on data with LOCF
Mean change from baseline in Pruritus Numeric Rating Scale (NRS) score at Week 16	ANCOVA model adjusted by baseline NRS score, treatment, stratification factor on data with MI	ANCOVA model adjusted by baseline NRS score, treatment, stratification factor on data with LOCF
Mean change from baseline in skin discomfort/pain Visual Analog Scale (VAS) at Week 16	ANCOVA model adjusted by baseline VAS score, treatment, stratification factor on data with MI	ANCOVA model adjusted by baseline VAS score, treatment, stratification factor on data with LOCF
Proportion of subjects who achieve Psoriasis Area Severity Index (PASI) < 3 at Week 16	CMH test adjusting for the stratification factor on data with MI	CMH test adjusting for the stratification factor on data with LOCF and data with NRI
Proportion of subjects who achieve Patient Benefit Index (PBI) global score of ≥ 1 at Week 16	CMH test adjusting for the stratification factor on data with MI	CMH test adjusting for the stratification factor on data with LOCF and data with NRI
Mean percent change from baseline in European Quality of	ANCOVA model adjusted by baseline EQ-5D score*, treatment,	ANCOVA model adjusted by baseline EQ-5D score*, treatment,

Apremilast

Statistical Analysis Plan. Protocol CC-10004-PSOR-020

Amgen INC.

Life 5-Dimension (EQ-5D) score* at Week 16	stratification factor on data collected on scheduled Week 16 visit	stratification factor on end of phase assessment

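### The Week 16 DLQI-change ANCOVA adjusts for one pre-randomisation DLQI although two are collected; adding the screening value would give a small, low-cost gain in precision

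*Protocol*

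**What the plan says.** - **Two readings before randomisation.** Protocol 6.1 includes in the screening visit "Health-related quality of life and efficacy assessments to determine study eligibility, including DLQI". Table 3 marks the DLQI at Screening, up to 35 days before randomisation, and again at Week 0.
- **Entry.** Inclusion criterion 6 reads "Subject has a DLQI score > 10 at baseline", so the Week 0 reading is truncated from below.
- **Baseline.** SAP 5.4 states that for efficacy "baseline is defined as the last value measured prior to or at the randomization visit". That is Week 0 when present; the screening value serves only if Week 0 is missing.
- **Analysis.** SAP Table 5 gives the primary analysis of DLQI change as "ANCOVA model adjusted by baseline DLQI score, treatment, stratification factor on data with MI". SAP 9.2 places this endpoint directly after the primary in the hierarchical sequence.
- **Imputation.** SAP 9.3 examines missing-data patterns "at the core baseline (Week 0), Week 2, Week 4, and Week 16". Its regression step states: "The missing values at each visit will be imputed based on treatment, stratification factor, and DLQI scores at the core baseline and previous visits". Screening is not among the visits listed.
- **Primary test.** The CMH test of the 4-point response is stratified by manifestation and has no baseline covariate.

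**The concern.** Once an analysis adjusts for baseline, a second pre-treatment reading of the same score improves it whenever that reading predicts Week 16 beyond Week 0 and the other terms. One DLQI score carries visit-to-visit noise. Here it is also the score on which subjects are selected, and this narrows its range and weakens its relation to Week 16. The screening DLQI is already in the database, precedes randomisation and needs no extra visit.

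What is at stake is the standard error of one secondary comparison. That comparison matters more than most secondaries because a non-significant result there stops formal claims for every endpoint below it in SAP 9.2.

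**Working it through.** **1. The plan's own figures.** For 0.70 vs 0.50, two-sided 0.05, 140:70, the normal approximation gives power 0.802 (unpooled) or 0.807 (pooled); the plan states 0.807. At 255 subjects it gives 0.872 (unpooled), as the protocol states. Inflation: 210/0.76 = 276.3, against 276 in the SAP. These figures concern the unadjusted responder test, so they set the context and are not in dispute.

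**2. Formula.** Let ρ be the correlation of each pre-treatment reading with Week 16 and r the correlation between the two readings. If the readings are exchangeable, R² with one is ρ² and with two is 2ρ²/(1+r). The residual-variance ratio is [1 − 2ρ²/(1+r)] / (1 − ρ²).

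Example, ρ = 0.5 and r = 0.7: R² rises from 0.25 to 0.5/1.7 = 0.294. The ratio is 0.706/0.75 = 0.941, so the standard error falls by 3.0%.

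**3. Assumed variances.** Take screening = T + e₁, Week 0 = T + e₂, Week 16 = T − 5 + c + e₃, with SD of T 4-5, visit SD 2.5-3.5 and SD of true change c 4-6. Then r = T²/(T²+e²) and ρ = T²/√[(T²+e²)(T²+c²+e²)], where the letters stand for SDs.

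- Smallest gain (4, 2.5, 6): r = 16/22.25 = 0.719, ρ = 16/√(22.25 × 58.25) = 0.444, ratio 0.960.
- Largest gain (5, 3.5, 4): r = 25/37.25 = 0.671, ρ = 25/√(37.25 × 53.25) = 0.561, ratio 0.910.

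**4. Selection.** Truncating at Week 0 DLQI > 10 leaves these ratios essentially unchanged, because Week 0 is already in the model. Simulation with mean 14 gives cuts of 4.0-9.0%. If screening must also exceed 10, the cuts are 3.1-6.6%. Hence about 3-9% overall, or 1.5-4.6% in standard error (1 − √0.97 to 1 − √0.91).

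Selection does weaken the single baseline. With an assumed latent mean of 13, SD 6, ρ = 0.5 and r = 0.7, its R² falls from 0.25 to 0.14, and adding screening raises it to 0.19.

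**5. Washout.** Consent, and so screening, can precede washout from prior medication (Table 3, footnote e). Adding noise of SD 3-5 to the screening reading in step 3 gives cuts of 0.7-6.3%.

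A harsher case uses unequal correlations: a = 0.5 for Week 0, b = 0.30-0.40 for screening, r = 0.5-0.7, with R² = (a² + b² − 2abr)/(1 − r²). For b = 0.4, r = 0.6: 0.17/0.64 = 0.266, ratio 0.979. For b = 0.3, r = 0.6: 0.16/0.64 = 0.25, ratio 1.000. The gain here is about 0-2%.

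**6. What it does to power.** Assume normal change with equal SDs. Responder rates of 0.50 and 0.70 then correspond to a shift of 0.524 SD. With 140:70 the standard error is √(1/140 + 1/70) = 0.1464 SD, so z = 3.58 and power is Φ(3.58 − 1.96) = 0.948, before any baseline adjustment. Variance cuts of 2%, 3% and 9% give 0.951, 0.953 and 0.964. At the 0.50 vs 0.83 seen in the earlier Phase 3 subset, power is about 1.

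**7. Imputation.** With an assumed partial response at Weeks 2 and 4, adding screening cuts the Week 16 residual variance by at most about 2.6% given Week 2, and by at most about 1.5% once Weeks 2 and 4 are both observed. Only subjects with no post-baseline DLQI gain appreciably.

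**The case against.** The strongest reply is that single-baseline ANCOVA is standard, nothing in the plan is biased or contradictory, and at about 0.95 power the change is unlikely to alter a decision. That stands, and it is why the point is an optional refinement. It does not remove the gain, because the covariate receives only the weight the data support and, being pre-randomisation, cannot bias the comparison.

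A reader might infer more than the documents support:

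- **That the screening DLQI is used nowhere.** It helps decide eligibility and is the fallback baseline under SAP 5.4.
- **That it is an independent reading of the subject's usual level.** It may be selected too. Topicals must stop 2 weeks, and phototherapy and conventional systemics 4 weeks, before randomisation, while screening can be up to 35 days before. Some screening scores may therefore be on-treatment scores.
- **That the gain is worth 9 to 27 of the 276 subjects** (276 × 0.03/0.97 to 276 × 0.09/0.91). The 276 was set for the responder CMH test, which has no baseline covariate.
- **That imputation is where it helps most.** Weeks 2 and 4 already carry most of the information. Leavers are asked to attend an Early Termination visit, and any assessment on days 2-21 maps to Week 2, so few subjects may lack a post-baseline score.

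The cost argument against the MCMC step also stands. It runs by arm and stratum, with placebo cells averaging 92/5 ≈ 18 subjects. A fifth variable raises the parameters per cell from 4 + 10 = 14 to 5 + 15 = 20, which makes the SAP's fallback to pooling more likely.

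**Conclusion.** The point holds as a minor improvement. The Week 16 DLQI-change ANCOVA leaves a small amount of precision unused by ignoring a second pre-randomisation DLQI. The expected cut in residual variance is about 3-9% if the readings are exchangeable and about 0-6% if washout makes screening less predictive. All of this rests on assumed variances and correlations, since the documents give none.

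The gain applies to the secondary DLQI-change analysis. The primary CMH could benefit only through imputation, and there only slightly. The same idea could be raised for PASI, also scored at both visits, but PASI < 3 is analysed by CMH, so only its imputation could gain, and no size has been established for that.

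**What to change.** In SAP 9.4.1 and Table 5, add screening DLQI as a separate second covariate in the Week 16 DLQI-change ANCOVA; do not average it into baseline. Specify:

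- the value comes from the screening that led to randomisation, since Protocol 6.1 allows one re-screening;
- where the screening DLQI is missing, the Week 0 value is used in its place;
- the Week 0 baseline, the change score and the 4-point response definition do not change.

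Optionally, add it as a predictor in the predictive-mean-matching step (SAP 9.3 and 9.4.1), which also keeps that step in line with the ANCOVA. Leave it out of the by-arm-by-stratum MCMC step.

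The cost is a few lines of SAP text, about one degree of freedom and no new data. The change should be made before the SAP is signed, which SAP section 2 sets before the Week 16 data transfer. If that has passed, run it as a labelled supportive analysis.
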